11.8 Health Economics

Not applicable

11.9 Interim Analyses

[figure not shown]
Not applicable

11.10 Sample Size Justification

Sample size calculation for each of the relevant efficacy endpoints is described below.

Primary Efficacy:

Sample size calculation for the primary efficacy hypothesis on decrease in symptomatology is based on published data (Chalmers 2012). With an assumed SD for paired differences of 10, a sample size of 36/sequence will provide 80% power to detect a difference of 3 at one-sided $\alpha=0.05$.

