8 SUBJECT POPULATION

Approximately 120 subjects (approximately 8 to 20 subjects per site) are to be randomized at approximately 9 United States (US) sites to achieve approximately 110 subjects completed. An advertisement may be used to aid recruitment. The advertisement will be submitted to the IEC/IRB for approval. The IRB approved Pre-screening questionnaire will be provided before taking the consent.

The enrollment for the study is planned for 6 weeks. The expected duration of subject participation in the study (3 scheduled visits) is 30 ± 3 days per study period (up to 66 days total). The complete inclusion and exclusion criteria are presented in Section [8.1](#) and Section [8.2](#).

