11.4.1.2 Analysis Methods

A mixed effect repeated measures model will be fit to test these hypotheses, including terms for lens care solution, period, sequence group, and baseline CLDEQ-8 as fixed effects and subject as a random effect. Lens care difference (CCP minus HMPS) and the corresponding one-sided 95% upper confidence limit will be provided.

Descriptive summary statistics will also be presented for the subgroup of habitual BIOTRUE formulation users.

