Short Title:

**Statistical Analysis Plan
LCS739-P001**

Full Title:

**Statistical Analysis Plan
LCS739-P001 / NCT02965833**

Protocol Title: Clinical Study of CLEAR CARE® PLUS for Presbyopic Contact Lens Wearers

Project Number: LCS739-P001

Protocol TDOC Number: TDOC - 0052880

Author: [REDACTED]

[REDACTED]

Template Version: Version 4.0, approved 16MAR2015

Approvals: See last page for electronic approvals.

Job Notes:

This is the original (Version 1.0) Statistical Analysis Plan for this study. This version of the Statistical Analysis Plan is based on Version 1.0 of the study protocol.

Executive Summary:

Key Objectives:

The primary objective is to demonstrate superiority of CLEAR CARE PLUS (CCP) cleaning & disinfecting solution when compared to the subject's habitual multipurpose solution (HMPS) in reducing symptoms of contact lens induced dryness after 30 days of use, based on responses to the CLDEQ-8 (abbreviated Contact Lens Dry Eye Questionnaire).

Decision Criteria for Study Success:

Success of this study will be based on demonstration of superiority of CCP cleaning & disinfecting solution compared to habitual MPS in reducing symptoms of contact lens induced dryness after 30 days of use, based on responses to the CLDEQ-8.

Table of Contents

Statistical Analysis Plan LCS739-P001	1
Table of Contents	3
List of Tables.....	4
List of Figures	4
1 Study Objectives and Design.....	5
1.1 Study Objectives.....	5
1.2 Study Description	6
1.3 Randomization.....	8
1.4 Masking	8
1.5 Interim Analysis	9
2 Analysis Sets.....	9
2.1 Safety Analysis Set.....	9
2.2 Full Analysis Set.....	9
2.3 Per Protocol Analysis Set	9
3 Subject Characteristics and Study Conduct Summaries.....	9
4 Efficacy Analysis Strategy.....	10
4.1 Efficacy Endpoints	10
4.2 Efficacy Hypotheses	11
4.2.1 Hypothesis for the Primary Endpoint	11
[REDACTED]	12
4.3 Statistical Methods for Efficacy Analyses.....	13
4.3.1 Primary Efficacy Analyses	13
[REDACTED]	13
[REDACTED]	15
4.5 Subgroup Analyses and Effect of Baseline Factors.....	16
4.6 Interim Analysis for Efficacy	16
5 Safety Analysis Strategy	16
5.1 Safety Endpoints.....	16
5.2 Safety Hypotheses	17
5.3 Statistical Methods for Safety Analyses	17

5.3.1	Adverse Events.....	17
5.3.2	Biomicroscopy Findings.....	18
5.3.3	Device Deficiencies.....	18
6	Analysis Strategy for Other Endpoints.....	18
7	Sample Size and Power Calculations	18
8	References	19
9	Revision History.....	19
10	Appendix	20

List of Tables

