4.2 Efficacy Hypotheses

4.2.1 Hypothesis for the Primary Endpoint

[figure not shown]
The primary hypothesis to be tested is that CCP is superior to HMPS in reducing dryness symptomatology as measured by CLDEQ-8.

[figure not shown]
The null and alternative hypotheses for the primary efficacy endpoint are formulated as follows:

$$H_0: \mu_{(CCP)} - \mu_{(HMPS)} \geq 0$$

$$H_a: \mu_{(CCP)} - \mu_{(HMPS)} < 0$$

where $\mu_{(CCP)}$ and $\mu_{(HMPS)}$ denote the mean CLDEQ-8 score for CCP and HMPS, respectively, at the Day 30 follow-up.

[figure not shown]

[figure not shown]

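### Is one-sided alpha 0.05 with power stated for 72 subjects a flaw, when 110 completers are required and one-sided 0.025 looks affordable?

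*Protocol*

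**What the plan says.** The SAP's Executive Summary rests the study on one comparison: "Success of this study will be based on demonstration of superiority of CCP cleaning & disinfecting solution compared to habitual MPS". SAP 4.2.1 puts it as a directional claim: "The primary hypothesis to be tested is that CCP is superior to HMPS in reducing dryness symptomatology as measured by CLDEQ-8". Protocol 11.4.1.1 and SAP 4.2.1 give the same one-sided null and alternative for the mean CLDEQ-8 score, CCP minus habitual solution, with no margin beyond zero. Protocol 11.4.1.2 says that "the corresponding one-sided 95% upper confidence limit will be provided" for that difference.

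The sample size text is the same in Protocol 11.10 and SAP 7. Taking 10 as the SD of the paired differences, both state that "a sample size of 36/sequence will provide 80% power to detect a difference of 3 at one-sided" level, with alpha set to 0.05. The synopsis repeats these figures. The recruitment target is larger. Protocol 8 plans about 120 randomized subjects "to achieve approximately 110 subjects completed", and the synopsis lists 110 completed as the required number. No interim analysis is planned (Protocol 11.9, SAP 1.5 and 4.6) and there is no secondary efficacy objective (Protocol 11.4.2).

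**The concern.** Two features stand out. First, a one-sided 0.05 test allows twice the false-positive risk, in the direction of a CCP benefit, of a two-sided 95% interval that must exclude zero. A result could be declared superior while that interval still included zero. Second, the stated 80% belongs to 72 subjects, but 110 are to complete. The visible text gives neither the power at 110 nor a reason for choosing 0.05.

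Together these suggest a trial with power to spare and a low bar. At 110 completers, an observed difference of about 1.6 points would count as success, roughly half the 3-point planning effect on a 0 to 37 scale. The outcome is self-reported, and subjects know which solution is their own, so a modest reporting bias might carry the result over the line. If a stricter level really cost nothing, leaving alpha at 0.05 would be hard to defend.

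**Working it through.** **Inputs.** Difference 3, SD of paired differences 10, one-sided alpha 0.05 and 36 per sequence (Protocol 11.10, SAP 7, synopsis). 110 completed and about 120 randomized (synopsis, Protocol 8).

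**Method.** In a two-period crossover, the standard error of the treatment difference is SD/√N, with N the total number of subjects. The noncentrality is 3√N/SD, and power comes from the noncentral t distribution with N − 2 degrees of freedom.

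**1. The plan's own figure.** N = 2 × 36 = 72. The standard error is 10/√72 = 1.179, the noncentrality 3/1.179 = 2.546 and the critical t (70 df) 1.667. Power is 81.0% (81.6% by the normal approximation). The smallest N reaching 80% is 71, which rounds up to 36 per sequence. The stated figure reproduces.

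**2. Power at the planned size, SD 10.**

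| N | one-sided 0.05 | one-sided 0.025 |
|---|---|---|
| 72 | 81.0% | 70.9% |
| 110 | 93.1% | 87.7% |
| 120 | 94.8% | 90.3% |

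**3. Dependence on the SD.** N = 110, difference 3.

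| SD | one-sided 0.05 | one-sided 0.025 |
|---|---|---|
| 10 | 93.1% | 87.7% |
| 11 | 88.4% | 80.9% |
| 12 | 83.2% | 73.8% |

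A true difference of 2.5 with SD 10 gives the same pair as SD 12, because 2.5/10 = 3/12. If the SD is 20% above the assumption, 0.05 still meets the stated 80% and 0.025 does not.

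**4. Smallest significant difference.** N = 110, standard error 10/√110 = 0.953.
- One-sided 0.05: 1.659 × 0.953 = 1.58 points.
- One-sided 0.025: 1.982 × 0.953 = 1.89 points.
- Change: 0.31 points.

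**5. Effect on reporting bias.** Assume, for illustration only, no true effect and a bias of 1.5 points towards CCP. The noncentrality is 1.5/0.953 = 1.573. The chance of a false success is 46.8% at 0.05 and 34.4% at 0.025. The stricter level leaves most of that risk in place.

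**6. Consistency of the alpha.** The hypotheses are directional (Protocol 11.4.1.1, SAP 4.2.1). The alpha is one-sided 0.05 in the synopsis, Protocol 11.10 and SAP 7. The reported limit is a one-sided 95% limit (Protocol 11.4.1.2), which is the interval matching that test. With no interim analysis, no alpha is spent elsewhere. These statements agree with one another.

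**7. The gap between 72 and 110.** Protocol 11.10 and SAP 7 both announce a calculation for each relevant efficacy endpoint, in the plural, but show only the primary one. Text is blacked out directly after the mention of the primary endpoint in Protocol 11.4 and SAP 4. The SAP's table of contents has a redacted entry beneath its efficacy hypotheses. A calculation that sets 110 may stand in the hidden text.

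**The case for a change.** The strongest case for the concern is that feasibility, the usual defence of a lenient alpha, does not apply here. At 72 subjects, 0.025 would give only 70.9% power. At 110 it gives 87.7%, and 90 completers would already give 80.4%. Halving the false-positive rate from 5% to 2.5% then costs 93.1 − 87.7 = 5.4 points of power. It would also spare the sponsor a superiority claim whose two-sided 95% interval includes zero, which at SD 10 happens for observed differences between 1.58 and 1.89. The single decisive endpoint is subjective and the masking of subjects is only partial.

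The arithmetic stands, and many statisticians would prefer 0.025. It is also true that the visible text gives no reason for 0.05 and no power at 110. But nothing in the documents calls for the stricter level. Protocol 5.1 describes market support for a solution that FDA has already cleared, so the error rate is a disclosed design choice. The claim that the change is nearly free holds only if the SD is close to 10, a value taken from a published source that cannot be checked here. Bias from partial masking, which Protocol 9.3 and 9.4 acknowledge, is not removed by a threshold 0.31 points higher. Stating the power at 110 would add information but would change no result or conclusion.

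**Conclusion.** The concern does not hold. The plan's power statement is correct for the sample size it names (81.0% against a stated 80%), and one-sided 0.05 is prespecified and applied consistently. Moving to 0.025 at 110 completers would trade 5.4 points of power for a lower false-positive rate if the SD is 10. If the SD is 12 it would cost 83.2 − 73.8 = 9.4 points and take power below 80%. Reasonable statisticians differ on that trade.

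The additional subjects cannot be called surplus, because the calculation behind 110 may be redacted. The power figures take the plan's difference of 3 points as given and read 36 per sequence as subjects who contribute both periods, as the use of paired differences implies.

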12 ADVERSE EVENTS AND DEVICE DEFICIENCIES

12.1 General Information

An AE is any untoward medical occurrence, unintended disease or injury, or untoward clinical signs (including abnormal laboratory findings) in subjects, users, or other persons, whether or not related to the investigational medical device (test article). Refer to the Glossary of Terms for categories of AEs and SAEs.

Figure 12-1 Categorization of All Adverse Events

[figure not shown]
[figure not shown]

Figure 12-2

Categorization of All Serious Adverse Events

Any other potentially sight-threatening event may also be considered serious based on the judgment of the Investigator and should be reported appropriately as delineated in Section 12.3.

Device Deficiencies

A device deficiency may or may not be associated with subject harm (ie, ADE or SADE); however, not all ADEs or SADEs are due to a device deficiency. The Investigator should determine the applicable category for the identified or suspect device deficiency and report any subject harm separately.

- Failure to meet product specifications
- Solution cloudy
- Packaging deficit (eg, mislabeled product, tampered seal, leaking bottle/container)
- Suspect product contamination
- Lack of performance

12.2 Monitoring for Adverse Events

At each visit, after the subject has had the opportunity to spontaneously mention any problems, the Investigator should inquire about AEs by asking the standard questions:

- “Have you had any health problems since your last study Visit?”
- “Have there been any changes in the medicines you take since your last study Visit?”

Changes in any protocol-specific parameters and questionnaires evaluated during the study are to be reviewed by the Investigator. Any untoward (unfavorable and unintended) change in a protocol-specific parameter or questionnaire response that is clinically relevant, in the opinion of the Investigator, is to be reported as an AE. These clinically relevant changes will be reported regardless of causality.

12.3 Procedures for Recording and Reporting

AEs are collected from the time of informed consent. Any pre-existing medical conditions or signs/symptoms present in a subject prior to the start of the study (ie, before informed consent is signed) are not considered AEs in the study and should be recorded in the Medical History section of the eCRF.

- All SAEs must be reported immediately (within 24 hours) of the Investigator's or site's awareness.
- ADEs that do not meet seriousness criteria and device deficiencies must be reported within 10 calendar days of the Investigator's or site's awareness.
- A printed copy of the completed ***Serious Adverse Event and Adverse Device Effect*** and/or ***Device Deficiency*** eCRF must be included with product returns.
- Additional relevant information after initial reporting must be entered into the eCRF as soon as the data become available.
- Document any changes to concomitant medications on the appropriate eCRFs.
- Document all relevant information from Discharge Summary, Autopsy Report, Certificate of Death, etc, if applicable, in narrative section of the Adverse Device Effect (for related AEs) and Serious Adverse Event eCRF.

Note: Should the EDC system become non-operational, the site must complete the appropriate paper ***Serious Adverse Event and Adverse Device Effect*** and/or ***Device Deficiency*** Form. The completed form is faxed or emailed to the Study Sponsor at

according to the timelines outlined above; however, the reported information must be entered into the EDC system once it becomes operational.

Any AEs and device deficiencies for non-study marketed devices/products will be considered and processed as spontaneous (following the postmarket vigilance procedures) and should be communicated to the device's/product's manufacturer as per local requirements.

Study Sponsor representatives may be contacted for any protocol-related question and their contact information is provided in the Manual of Procedures that accompanies this protocol.

Further, depending upon the nature of the AE or device deficiency being reported, the Study Sponsor may request copies of applicable portions of the subject's medical records. The Investigator must also report all AEs and device deficiencies that could have led to a SADE according to the requirements of regulatory authorities or IRB/IEC.

12.4 Intensity and Causality Assessments

Where appropriate, the Investigator must assess the intensity (severity) of the AE based on medical judgment with consideration of any subjective symptom(s), as defined below:

Intensity (Severity)

Mild	An AE is mild if the subject is aware of but can easily tolerate the sign or symptom.
Moderate	An AE is moderate if the sign or symptom results in discomfort significant enough to cause interference with the subject's usual activities.
Severe	An AE is severe if the sign or symptom is incapacitating and results in the subject's inability to work or engage in their usual activities.

For every AE in the study, the Investigator must assess the causality (Related or Not Related to the medical device or study procedure). An assessment of causality will also be performed by Study Sponsor utilizing the same definitions, as shown below:

Causality

Related An AE classified as related may be either definitely related or possibly related where a direct cause and effect relationship with the medical device or study procedure has not been demonstrated, but there is a reasonable possibility that the AE was caused by the medical device or study procedure.

Not Related An AE classified as not related may either be definitely unrelated or simply unlikely to be related (ie, there are other more likely causes for the AE).

The Study Sponsor will assess the AEs and may upgrade the Investigator's assessment of seriousness and/or causality. The Study Sponsor will notify the Investigator of any AEs that are upgraded from non-serious to serious or from unrelated to related.

12.5 Return product analysis

Study Sponsor representatives and their contact information are provided in the Manual of Procedures that accompanies this protocol.

Alcon products associated with device deficiencies and/or product-related AEs should be returned and must include the Complaint # which will be provided by Study Sponsor after the case is entered in the Study Sponsor's Global Product Complaint Management System (GPCMS).

12.6 Unmasking of the Study Treatment

Masked information on the identity of the assigned medical device should not be disclosed during the study. If the treatment code needs to be broken in the interest of subject safety, the Investigator is encouraged to contact an appropriate Study Sponsor representative prior to unmasking the information if there is sufficient time. Dependent upon the individual circumstances (ie, medical emergency), the code may be broken prior to contact with the Study Sponsor. The Study Sponsor must be informed of all cases in which the code was broken and of the circumstances involved. Additionally, the Study Sponsor may be required to unmask the information in order to fulfill expedited regulatory reporting requirements.

12.7 Follow-Up of Subjects with Adverse Events

The Investigator is responsible for adequate and safe medical care of subjects during the study and for ensuring that appropriate medical care and relevant follow-up procedures are maintained after the study.

The Investigator should provide the Study Sponsor with any new safety information (which includes new AEs and changes to previously reported AEs) that may affect the safety evaluation of the device. For AEs that are unresolved/ ongoing at time of subject exit from study, any additional information received at follow-up should be documented in the eCRFs up to study completion (ie, database lock).

All complaints received after this time period will be considered and processed as spontaneous (following the postmarket vigilance procedures) and should be communicated to the medical device's manufacturer as per local requirements.

The Investigator should also report complaints on non-Alcon products directly to the manufacturer as per the manufacturer's instructions or local regulatory requirements.

12.8 Pregnancy in the Clinical Trial

Pregnancy should be included in the Medical History section of the eCRF when a woman becomes pregnant during the study. Pregnancy is not reportable as an AE; however, complications may be reportable and will be decided on a case-by-case basis.

13 DATA HANDLING AND ADMINISTRATIVE REQUIREMENTS

13.1 Completion of Source Documents and Case Report Forms

The nature and location of all source documents will be identified to ensure that original data required to complete the eCRFs exist and are accessible for verification by the site monitor. If electronic records are maintained, the method of verification must be determined in advance of starting the study. At a minimum, source documents should include the following information for each subject:

- Subject identification (name, sex, race/ethnicity)
- Documentation of subject eligibility
- Date of informed consent
- Dates of visits
- Documentation that protocol specific procedures were performed
- Results of study parameters, as required by the protocol
- Trial medication accountability records
- Documentation of AEs and other safety parameters (if applicable)
- Records regarding medical histories and the use of concomitant therapies prior to and during the study
- Date of trial completion and reason for early discontinuation, if applicable
- Pre-screening Questionnaire Responses
- Manifest Refraction and BCVA (as needed)
- Compliance with study and study regimen
- Planned and unplanned lens replacement dates

It is required that the author of an entry in the source documents be identifiable. Direct access to source documentation (medical records) must be allowed for the purpose of verifying that the data recorded on the eCRF are consistent with the original source data.

Electronic CRFs (eCRFs) will be provided to the sites; only designated individuals may complete the eCRFs. The eCRFs will be submitted at regular intervals based upon the clinical trial visit schedule. It is expected that all data reported will have corresponding entries in the source documents and that the Principal Investigator will review the reported data and certify

that the eCRFs are accurate and complete. No subject identifiers should be recorded on the eCRFs beyond subject number, and demographic information.

Deviations from this protocol, regulatory requirements, and GCP must be recorded in the study records. An explanation of the deviation should be included, as applicable. In addition, corrective and preventive action should be identified, implemented, and documented within the study records.

13.2 Data Review and Clarifications

Targeted eCRF data will be reviewed against the subject's source data by the study monitors according to the SDV plan to ensure completeness and accuracy. After monitoring has occurred at the clinical sites and the eCRFs have been submitted, additional data clarifications and/or additions may be needed. Data clarifications and/or additions are documented and are part of each subject's eCRFs.

13.3 Regulatory Documentation and Records Retention

The Investigator is required to maintain up-to-date, complete regulatory documentation as indicated by the Sponsor and the Investigator's files will be reviewed as part of the ongoing study monitoring. Financial information is not subject to regulatory inspection and should be kept separately.

Additionally, the Investigator must keep study records and source documents until the Sponsor provides written approval for their destruction. If the Investigator retires, relocates, or for any other reason withdraws from responsibility of keeping the study records, the Sponsor must be notified and suitable arrangements made for retention of study records and source documents needed to comply with national and international regulations (generally 2 years after discontinuing clinical development or after the **latest** marketing approval).

